## 2. LIST OF ABBREVIATIONS

See Medicine Glossary:

<http://glossary>

Term	Definition / description
ADS	Analysis Data Set
AE	Adverse event
ANCOVA	Analysis of Covariance
ATC	Anatomical Therapeutic Classification
AUC	Area Under the Curve
BRPM	Blinded report planning meeting
CD	Concomitant diagnosis
CML	Clinical Monitor Local
COPD	Chronic Obstructive Pulmonary Disease
CRA	Clinical Research Associate
CT	Concomitant treatment
CTP	Clinical Trial Protocol
CTR	Clinical Trial Report
DBL	Data Base Lock
DH	Digital Health
DM&SM	Boehringer Ingelheim Data Management and Statistics Manual
DRA	Drug Regulatory Affairs
eCRF	electronic Case Report Form
EoT	End of Text
EMEA	European Agency for the Evaluation of Medicinal Product
FAS	Full analysis set
FDC	Fixed Dose Combination
FEV 1	Forced Expiratory Volume in One Second
FVC	Forced Vital Capacity
ICF	Informed Consent Form
ICH	International Conference on Harmonisation

Term	Definition / description
(I)PD	(Important) Protocol Deviation
(I)PV	(Important) Protocol Violation
IVRS	Interactive Voice Response System
LOCF	Last observation carried forward
MedDRA	Medical Dictionary for Regulatory Activities
MMRM	Mixed effects model repeated measures
MQRM	Medical Quality Review Meeting
PEF	Peak Expiratory Flow
PFT	Pulmonary Function Test
PIFR	Peak Inspiratory Flow Rate
PK	Pharmacokinetics
PPS	Per protocol set
PRN	Pro re nata (when necessary)
PSTAT	Project Statistician
PT	Preferred term
Q1	Lower quartile
Q3	Upper quartile
REML	Restricted maximum likelihood
RS	Randomised set
SABA	Short-acting beta agonist
SAE	Serious Adverse Event
SAMA	Short-acting muscarinic antagonist
SD	Standard deviation
SMQ	Standardised MedDRA query
SOC	System organ class
TS	Treated set
TSAP	Trial statistical analysis plan
TTM	Termination of trial medication

### **3. INTRODUCTION**

As per International Conference on Harmonisation (ICH) E9 ([1](#)) , the purpose of this document is to provide a more technical and detailed elaboration of the principal features of the analysis described in the protocol, and to include detailed procedures for executing the statistical analysis of the primary and secondary variables and other data.

This Trial Statistical Analysis Plan (TSAP) assumes familiarity with the Clinical Trial Protocol (CTP), including Protocol Amendments. In particular, the TSAP is based on the planned analysis specification as written in CTP Section 7 “Statistical Methods and Determination of Sample Size.” Therefore, TSAP readers may consult the CTP for more background information on the study, e.g., on study objectives, study design and population, treatments, definition of measurements and variables, planning of sample size, randomisation.

SAS® Version 9.4 or later will be used for all analyses.

## **4. CHANGES IN THE PLANNED ANALYSIS OF THE STUDY**

Sensitivity analyses were added for primary and key secondary analyses in section 7.4.2 and 7.5.1. The analysis of further endpoint includes MMRM analysis.

## **5. ENDPOINTS(S)**

### **5.1 PRIMARY ENDPOINT(S)**

The primary endpoint is change from baseline in FEV1 AUC0-3h after 4 weeks of treatment.

Analyses will be performed in PIFR optimal ( $\geq 60$  L/min) group and PIFR sub-optimal ( $< 60$  L/min) group separately.

### **5.2 SECONDARY ENDPOINT(S)**

[figure not shown]
#### **5.2.1 Key secondary endpoint(s)**

The key secondary endpoint is change from baseline in trough FEV1 after 4 weeks of treatment.

Analyses will be performed in PIFR optimal ( $\geq 60$  L/min) group and PIFR sub-optimal ( $< 60$  L/min) group separately.

#### **5.2.2 Secondary endpoint(s)**

There are no additional secondary endpoints in this trial.

## **5.4 OTHER VARIABLE(S)**

### **Safety**

All adverse events (including those identified during the physical examination): Details can be found in section 7.8.1.

### **Treatment exposure/Time to discontinuation from study drug**

Treatment exposure will be calculated as drug stop date minus drug start date plus 1. Time to discontinuation of study drug is defined as discontinuation date minus drug start date plus 1.

### **Treatment compliance**

- Percent compliance
- Percent missing compliance information

Treatment compliance (80% to 120%) will be based on data recorded in the eCRF.

## **6. GENERAL ANALYSIS DEFINITIONS**

### **6.1 TREATMENT(S)**

[figure not shown]
As described in Section 4 of the CTP, the following treatments are planned to be investigated in this study:

Table **Error! No text of specified style in document.**: 1 Treatment and labels

Treatment	Label
Tiotropium + Olodaterol FDC (5 µg / 5 µg) inhalation solution	T+O 5/5
Matching Placebo inhalation solution	PBO

This trial is a randomized, double-blind, placebo-controlled, multicenter, parallel study designed to assess efficacy of tiotropium + olodaterol delivered by Respimat® on FEV1 AUC0-3h, and trough FEV1 in patients with moderate to severe COPD, stratified by optimal and sub-optimal PIFR. The study will consist of a screening period of up to 2 weeks, a 4-week randomized treatment period and a three week follow-up period. An overview of the trial design is presented in Figure 6.1: 1

Figure 6.1: 1 Trial Design

\*Stratification by PIFR (< 60 L/min [suboptimal] or ≥ 60 L/min [optimal])

The residual effect period is defined as 21 days.

Approximately 200 patients will be randomized (1:1) to either the active arm (tiotropium + olodaterol, FDC) or the placebo arm. The randomization will be stratified by optimal ( $\geq 60$  L/min) or sub-optimal (< 60 L/min) PIFR as measured with the [REDACTED] set

at med/low resistance. Each strata will be capped to a total of approximately 100 patients. An interactive response technology (IRT) will be used for randomization and stratification.

After signing informed consent and completing the screening visit, patients will enter a screening period of 3 to 14 days. During the screening period, patients will continue to receive their COPD maintenance treatment, except for the medication washout requirements required before the randomization visit. Patients will be randomized into the 4-week treatment period in which they will be randomly assigned to one of two treatments: tiotropium + olodaterol FDC or matching placebo. The randomization visit (visit 2) will be followed by a clinic visit in 2 weeks (visit 3) and end of treatment (EOT) visit (visit 4) will be 4 weeks (28 days) after randomization. A follow-up visit by telephone will be scheduled three weeks after the last dose of study medication.

## 6.2        IMPORTANT PROTOCOL DEVIATIONS

A patient's deviation (PD) from the trial protocol is considered "important" if it can be expected that the deviation had a distorting influence on the assessment of the treatment effect on the primary endpoint of the trial or could affect the patient's safety or rights.

Table 6.2:1 gives the important PDs for this trial. The final decision with regard to important PVs and exclusion from the PPS will be made at the final review meeting. Some important PVs will be set automatically; others will need a decision at a Medical Quality Review Meeting (MQRM) team review of the manual PD log.

The IQRMP addresses the risks of items related to COVID-19. The DV domain contains all iPd and relevant information regarding COVID-19. All iPd will be listed.

Table 6.2: 1    Handling of iPDs

iPD code	iPD Category & Brief Description	Requirement	Excluded from which analysis set
A1	Inclusion criteria not met	IN #2-7 (per protocol)	None
A2	Exclusion Criteria not met	EX #1-24 (per protocol)	None
B1	Informed consent not available/not done	IN #1. Verify that the subject has been properly consented and has signed re consent when applicable	All
B2	Informed consent too late	Verify that the subject has been properly consented and has signed re consent when applicable	None
C1	Incorrect trial medication taken	Incorrect trial medication taken	None
C2	Randomization order not	Verify correct dispensing of IMP by	None

	followed and incorrect trial medication taken	comparing IRT records against IMP Accountability Log	
C3.2	Non-compliance with study medication as defined in protocol section 4.3 Treatment Compliance	Serious non-compliance with study medication as defined in protocol 4.3 Treatment Compliance	None
C4	Medication code broken inappropriately	Medication code broken inappropriately	None
D1	Improper medication washout at baseline visit or at primary endpoint visit 4.	Verify that patients have complied with medication washout requirements prior to PFT measurements during V2 (baseline), V3 and V4 (primary endpoint) (protocol table 4.2.3.1.1 and footnotes)	None
D2	Prohibited medication use during the study	Prohibited medication use during study as per protocol section 4.2.3.1.1	None
F3.1	PFT measurement at 3-hour time point performed more than 4 hours after dosing	At visit 2, the PFTs should begin between 07: 00 a.m. and 10:00 a.m. At visits 3 and 4, PFTs should begin within ± 30 minutes of the time it started at visit 2.	None
F3.2	PFT measurement at 3:00 planned time performed earlier than 2 hours after dosing at primary endpoint visit(s)	At visit 2, the PFTs should begin between 07: 00 a.m. and 10:00 a.m. At visits 3 and 4, PFTs should begin within ± 30 minutes of the time it started at visit 2.	None
F4.1	Trial medication taken prior to pre-dose measurement at baseline visit	Verify that the visit has been rescheduled and the site has retrained the subject to dose only after the trough PFT measurement during V2.	None
F4.2	Trial medication taken prior to pre-dose measurement at primary endpoint visit(s)	Verify that the visit has been rescheduled and the site has retrained the subject to dose only after the trough PFT measurement during V4.	None
F4.4	Drug administration outside time window at randomization visit and primary endpoint visit.	Verify that the subject dosed 5 minutes prior to the first PFT measurement during V2 and V4.	None
Q1	Missed examinations; Non-COVID-19 related		None

Q2	Missed visit; Non-COVID-19 related		None
Q3	Drug shipment; Non-COVID-19 related		None
...	...		...

[figure not shown]
### 6.3 SUBJECT SETS ANALYSED

The following subject sets are defined in this trial:

- Randomized Set (RS): This patient set includes all patients who signed the informed consent form and were randomized, regardless whether the patient was treated with trial medication or not.
- Treated Set (TS): All randomized patients who were dispensed trial medication and were documented to have taken any dose of trial medication.
- Full Analysis Set (FAS): This patient set is nested within the TS and includes patients who had baseline and at least one post-baseline measurement for at least one efficacy endpoint(either a baseline and post-baseline primary endpoint or a baseline and a post-baseline key secondary endpoint) The FAS will be used for the primary analyses of the primary efficacy endpoint and for all other efficacy endpoints.

Table 6.3: 1 Subject sets analysed

Class of endpoint	Treated set	Subject set	
		FAS	RS
Primary and key secondary endpoints		primary analysis	
(other) Secondary and further endpoints		X	
Safety endpoints & treatment exposure	X		
Demographic/baseline endpoints	X		
Disposition		X	

## 6.5 POOLING OF CENTERS

This section is not applicable because center/country is not included in the statistical model.

## 6.6 HANDLING OF MISSING DATA AND OUTLIERS

Every effort should be made to collect complete data for each time point on each test day.

The REML-based MMRM model described in Sections 7.4.1 and 7.5.1 will handle missing data due to early drop outs or missing data in between visits which are assumed to be missing at random.

Adjusted multiple imputation will be used to handle missing data in a sensitivity analysis. Details are described in Section 7.4.1 and 7.5.1.2.

### FEV1 measurements

FEV1 measurements at individual time points that are flagged as unacceptable by the vendor will be set to missing prior to applying any missing data imputation rules. Missing FEV1 measurements at a given in-clinic visit will be imputed by the available data from the patient at that visit except for trough FEV1. Completely missing visits will not be imputed and will be handled through the MMRM statistical model except for cases where a patient discontinues due to an AE indicative of worsening of COPD. For the case of discontinuing due to an AE indicative of worsening of COPD, completely missing visits, missing data points will be imputed with the worst observation observed before discontinuation.

Discontinuation due to an AE indicative of worsening of COPD will be determined as follows.

- Check that the reason for discontinuation on the termination of trial medication is adverse event.
- Get the AE flagged by the investigator as the primary reason for discontinuation of trial medication.
- Check whether this AE belongs to the group of AEs identified as corresponding to either COPD exacerbation or lower respiratory disorders. This will be based on the BI system in place for grouping MedDRA preferred terms into medical concepts (currently referred to as pharmacovigilance endpoints).

Additional details on the imputation of missing data for specific cases are provided below:

- Any visit occurring more than one day after discontinuation of study medication which has non-missing data will not be used in the analysis.
- For patients taking a salbutamol (SABA) as rescue medication during Visit 2 and 4, any subsequent FEV1 measurements from the time of rescue use until time of rescue plus 8 hours (e.g., 2:17 to 10:17) will be set to missing and imputed by the worst non-missing (either observed or imputed) observation for that visit strictly prior to the administration of the rescue medication (even if it is a pre-dose value, either observed or imputed). If there are FEV1 measurements after the 8-hour window they will be considered valid and not imputed provided that they are not in the 8-hour window for a subsequent rescue medication use. If rescue medication is taken at any on-treatment in-clinic visit and there is no rescue medication time given, data for the entire visit will be considered missing and it will be handled the same way as the case where all measurements after rescue use are set to missing.

Missing safety data will not be imputed with the exception of missing AE dates which will be imputed according to BI standards (see Boehringer Ingelheim Data Management and Statistics Manual (DM&SM) "Handling of missing and incomplete AE dates.

## 6.7 BASELINE, TIME WINDOWS AND CALCULATED VISITS

The baseline value will be the measurement made prior to the first dosing at Visit 2. If there are more than one measurement of FEV1 available prior to randomization, the mean of the two pre-dose pulmonary function test measurements at Visit 2, prior to the administration of the first dose of the randomized treatment, is used as the baseline FEV1. Planned and actual study day will be included in the analysis data sets. These will both be calculated relative to the beginning of study as indicated in the following table (nominal visits). See Table 6.7:1.

Time windows will not be used but rather planned visits.

Table 6.7:1 Planned and actual study days

Visit	Planned Study Day	Actual Study Day
2	1	1
3	15	Visit 3 date – Visit 2 date + 1
4	29	Visit 4 date – Visit 3 date + 1

## 7. PLANNED ANALYSIS

For End-of-Treatment (EoT) tables, the set of summary statistics for descriptive displays of continuous variables is: N / Mean / SD / Min / Median / Max.

Tabulations of frequencies for categorical data will include all possible categories and will display the number of observations in a category as well as the percentage (%) relative to the respective treatment group (unless otherwise specified, all patients in the respective patient set whether they have non-missing values or not). Percentages will be rounded to one decimal place. The category missing will be displayed only if there are actually missing values.

The efficacy analysis will be performed in FAS.

For efficacy and safety analyses, patients will be analysed according to their planned treatment group.

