4.1.4 Drug assignment and administration of doses for each patient

Dispensing trial medication

At visit 2 the IRT will assign two Respimat® kits (one for treatment and one as reserve). At visit 3 the patient will bring in all treatment kits (including the reserve kits) that were dispensed at visit 2. If the reserve kit dispensed at visit 2 was used by the patient, a new reserve kit can be dispensed at visit 3. Each treatment kit will have a unique medication ID number. Trial medication will be dispensed to the patient by the investigator or a qualified site staff at these visits. The amount of trial medication dispensed will be recorded on the drug accountability forms. Patients must return all Respimat® kits at visit 4 which is the end of treatment period

The reserve kits allow the patient the flexibility of not having to return to the clinic immediately to replace a lost or malfunctioning inhaler. In the event that a patient may need additional inhalers and cartridges due to rescheduled visits, inhaler loss or malfunction, these will be supplied on an 'on demand' basis. Dispensing of these extra inhalers will also be managed via the IRT.

At home, if the patient forgets to take the morning dose of trial medication, the patient can take the morning dose up until 12:00 midnight. After 12:00 midnight, the patient should skip the dose for that day and take the next dose the following morning.

Priming of the Respimat® Inhaler

Each newly assembled Respimat® Inhaler has to be primed. Priming should not take place in the same room where the patient is inhaling trial medication. The inhaler should be primed by actuating it until an aerosol is visible plus three additional actuations. All priming actuations should be directed to the ground.

Once assembled, the shelf-life of the Respimat® Inhaler with trial medication is 3 months. Therefore, it is important to always enter the date of the cartridge insertion on the medication label of the Respimat® Inhaler immediately after the cartridge is inserted.

Dispensing rescue medication

Salbutamol will be dispensed to all patients when they complete the screening visit, and are eligible to enter the screening period. Patients will receive adequate supply of rescue medication until the end of treatment period. Rescue medication will not be provided for the follow-up period. Before using for the first time, one actuation should be released into the air to ensure the device is working.

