7.3.4 Safety analyses

Adverse events will be coded using the Medical Dictionary for Regulatory Activities (MedDRA) coding dictionary. Standard BI summary tables and listings will be produced. All adverse events with an onset between start of treatment and end of the REP, a period of 21 days after the last dose of trial medication, will be assigned to the treatment period for evaluation. All randomized patients who have taken at least one dose of study drug (i.e., the

treated set) will be included in the safety analysis. In general, safety analyses will be descriptive in nature and will be based on BI standards. No hypothesis testing is planned.

Statistical analysis and reporting of adverse events will concentrate on treatment-emergent adverse events. To this end, all adverse events occurring between start of treatment and end of the residual effect period will be considered 'treatment-emergent'. The residual effect period is defined as 21 days. Adverse events that start before first drug intake and deteriorate under treatment will also be considered as 'treatment-emergent'.

Frequency, severity, and causal relationship of adverse events will be tabulated by system organ class and preferred term after coding according to the current version of MedDRA.

All treated patients will be included in the safety analysis. In general, safety analyses will be descriptive in nature and will be based on BI standards. No hypothesis testing is planned.

Laboratory data will be analysed both quantitatively as well as qualitatively. The latter will be done via comparison of laboratory data to their reference ranges. Values outside the reference range as well as values defined as clinically relevant will be summarized.

Treatment groups will be compared descriptively with regard to distribution parameters as well as with regard to frequency and percentage of patients with abnormal values or clinically relevant abnormal values.

Vital signs, physical examinations, or other safety-relevant data observed at screening, baseline, during the course of the trial and at the end-of-trial evaluation will be assessed with regard to possible changes compared to findings before start of treatment.

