### **7.8        SAFETY ANALYSIS**

All safety analyses will be performed on the treated set.

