#### **7.8.1        Adverse Events**

Unless otherwise specified, the analyses of adverse events will be descriptive in nature. All analyses of AEs will be based on the number of subjects with AEs and NOT on the number of AEs.

For analysis multiple AE occurrence data on the CRF will be collapsed into an AE provided that all of the following applies:

- All AE attributes are identical (LLT, intensity, action taken, therapy required, seriousness, reason for seriousness, relationship, outcome)
- The occurrences were time-overlapping or time-adjacent (time-adjacency of 2 occurrences is given if the second occurrence started on the same day or on the day after the end of the first occurrence).

For further details on summarization of AE data, please refer to (13,14).

The analysis of adverse events will be based on the concept of treatment emergent adverse events. That means that all adverse events occurring between first drug intake till last drug intake + residual effect period (21 days) will be assigned to the randomized treatment. All adverse events occurring before first drug intake will be assigned to 'screening' and all adverse events occurring after the residual effect period will be assigned to 'post-treatment' (for listings only). Adverse events that start before first drug intake and deteriorate under treatment will also be considered as 'treatment-emergent'. For details on the treatment definition, see Section 6.1.

According to ICH E3 AEs classified as 'other significant' needs to be reported and will include those non-serious and non-significant adverse events with

- (i) 'action taken = discontinuation' or 'action taken = reduced', or
- (ii) marked haematological and other lab abnormalities or lead to significant concomitant therapy as identified by the Clinical Monitor/Investigator at a Medical Quality Review Meeting.

An overall summary of adverse events will be presented.

The frequency of subjects with adverse events will be summarized by treatment, primary system organ class and preferred term (mention MedDRA levels to be displayed in the tables). Separate tables will be provided for subjects with other significant adverse events according to ICH E3 and for subjects with serious adverse events.

The system organ classes will be sorted alphabetically, preferred terms will be sorted by frequency (within system organ class).

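### Safety is grouped by planned arm, so in any patient who took the other arm's medication, adverse events are attributed to a treatment that was not taken; a small, cheaply fixed weakness

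*SAP*

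**What the plan says.** The grouping rule is explicit. Protocol 7.3 and SAP 7 carry the same sentence: "For efficacy and safety analyses, patients will be analysed according to their planned treatment group". SAP 7.8.1 applies it to AEs: those between first intake and last intake plus the 21-day residual effect period "will be assigned to the randomized treatment".

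The safety population is the Treated Set (SAP 7.8: "All safety analyses will be performed on the treated set"). SAP 6.3 defines it as "All randomized patients who were dispensed trial medication and were documented to have taken any dose of trial medication". Entry depends on having taken a dose; which treatment it contained plays no part.

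SAP 6.2, Table 6.2: 1, lists deviation C1, "Incorrect trial medication taken", and deviation C2, in which the randomization order was also not followed. Neither removes a patient from any analysis set. The planned output for these deviations is a listing ("All iPd will be listed"). Neither document describes a safety display by treatment received, or a rule for a patient exposed to both treatments.

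Protocol 5.2 states that the trial has no safety endpoints. Protocol 7.3.4 makes the safety analysis descriptive: "No hypothesis testing is planned".

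**The concern.** Planned-arm grouping is right for efficacy, where it preserves the randomized comparison. A safety table answers a different question: what happened to people who inhaled the drug, against people who did not.

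The plan's safety framework already follows exposure in two respects. A patient enters the set by taking a dose, and the AE window is set by first and last intake plus a residual period that Protocol 1.2 gives as a property of the drug. Only the arm follows assignment. A placebo-assigned patient who inhaled active drug would therefore have AEs collected over the drug's residual window and reported under placebo. An active-assigned patient given placebo would produce the reverse error.

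At stake is the accuracy of the descriptive AE and exposure tables. They are the trial's only between-arm safety evidence, and no sensitivity display stands behind them.

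**Working it through.** **The plan's own figure.** The documents give no wrong-kit rate and no AE rates, so there is no safety figure to reproduce. The sample size in Protocol 7.6 does reproduce: a two-sample t-test with a 140 ml difference, SD 210 ml and two-sided alpha 0.05 needs a total of 98 per PIFR stratum and gives 90.4% power. This point leaves it unchanged, because efficacy stays grouped by planned arm.

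**Inputs.**
- Arm size: 50 per arm in each of two PIFR strata (Protocol 7.5), so 2 × 50 = 100 per arm.
- True AE risks, assumed: p_A = 30% on active and p_P = 20% on placebo.
- Swaps, assumed: a fraction f of each arm takes the other treatment for the whole period.

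**Formula.** The expected rates under planned-arm grouping are:
- active: (1 − f)·p_A + f·p_P
- placebo: (1 − f)·p_P + f·p_A
- difference: (1 − 2f)·(p_A − p_P)

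For f = 0.01, active is 0.99 × 30 + 0.01 × 20 = 29.9%, placebo is 0.99 × 20 + 0.01 × 30 = 20.1%, and the difference is 9.8 points.

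| Swaps per arm | Active, as planned | Placebo, as planned | Displayed difference | Factor 1 − 2f |
|---|---|---|---|---|
| 0 | 30.0% | 20.0% | 10.0 | 1.00 |
| 1 | 29.9% | 20.1% | 9.8 | 0.98 |
| 2 | 29.8% | 20.2% | 9.6 | 0.96 |
| 5 | 29.5% | 20.5% | 9.0 | 0.90 |
| 10 | 29.0% | 21.0% | 8.0 | 0.80 |

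Grouping by treatment received gives an expected 10.0 points in every row.

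**Errors in one direction only.** If m placebo patients took active drug, the placebo rate becomes (1 − m/100) × 20% + (m/100) × 30%. The difference is 9.9, 9.8 and 9.5 points for m = 1, 2 and 5.

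**Other assumed risks.** For 10% against 5%, one swap per arm shows 4.9 points instead of 5.0, and five show 4.5. For 5% against 1%, one swap shows 3.92 instead of 4.0, and five show 3.6. The factor does not depend on the risks.

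**The case against.** The strongest reply is that nothing here is contradictory or left open. Protocol and SAP state the same rule, safety is descriptive, and the trial is a Phase IV study of an approved regimen. Dispensing runs through the IRT: it assigns both the treatment and the reserve kit, each kit has its own medication number, and extra inhalers go through the same system (Protocol 4.1.4). C2 already involves checking dispensing against IRT and accountability records, and the deviation listing can be read beside the AE listings. All of this stands and keeps the point small. It does not remove it: followed exactly, the rule still places a cross-arm patient's AEs in the wrong column. SAP 7.8.1 also cites an internal AE-summarization standard that is not available here, but the SAP's explicit wording is assignment to the randomized arm.

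A reader might infer four stronger things that the documents do not support.

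- **Any wrong kit causes misattribution.** Only a kit containing the other arm's treatment does. Using one's own reserve kit is planned use, and C1 does not say that the incorrect medication came from the other arm.
- **Keeping C1 and C2 patients in the safety set is itself a fault.** Dropping treated patients from safety would be worse.
- **One swap can decide a rare serious event.** Two cases against none becomes one against one only if the swapped patient is one of the two cases. If one placebo patient took active drug and the two cases fall at random among the resulting 101 active-treated patients, that chance is 2/101, about 2%. The plan also has no safety decision rule for such a count to trigger.
- **The dilution always flatters the drug.** It shrinks a difference of either sign. Worsening of the underlying disease is recorded as an AE (Protocol 5.2.6.1.1), and long-acting bronchodilators are not permitted as concomitant medication during treatment (Table 4.2.3.1: 1). If worsening is commoner on placebo, dilution understates an advantage of the drug.

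**Conclusion.** The point holds as a limited weakness in an analysis definition. For any patient who took the other arm's medication, the plan attributes AEs to a treatment that was not taken, and the expected between-arm difference moves toward zero by the factor 1 − 2f under full swaps in both arms. The reduction is 2% of the difference with one swap per arm of 100, and 10% with five.

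These sizes rest on assumed swap counts and assumed AE risks, and on exposure to the wrong treatment for the whole period. The true number of swaps is not given and is probably low under IRT dispensing; at zero, the effect is nil. Power, the primary and key secondary analyses and the type I error control are untouched. The change is worth making because it is specific and cheap, not because a material distortion has been shown.

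**What to change.** 1. In Protocol 7.3 and SAP 7, limit the planned-treatment sentence to efficacy.
2. In SAP 7.7 and 7.8, summarise AEs and exposure on the Treated Set by treatment actually received, derived from IRT and drug accountability records. Change SAP 7.8.1 to match.
3. Pre-specify one subject-level rule for mixed exposure, so that each patient enters one denominator. For example, a patient who took any active dose is counted once, in the active arm, for the whole on-treatment period. A rule that splits a patient's follow-up at the first active dose would not fit, because SAP 7.8.1 counts subjects with AEs.
4. List every cross-arm C1 or C2 patient with all AEs and their dates relative to the wrong kit. This shows any event that preceded the wrong kit but was moved by the rule in step 3.

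The cost is one derived variable and the wording. The IRT and accountability comparison is already required for C2, and kit-level code numbers are already kept (Protocol 4.1.8). The safety arm sizes may then differ slightly from the randomized ones, which a table footnote can explain.
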